2.7.4.2 Vital signs

The summary of vital signs will only include on treatment data, which are defined as those vital sign measurements after the first dose of study treatment and on or before last dose + 84 days.

Analysis of the vital sign measurements using summary statistics for the change from BSL for each post-BSL visit will be performed. These descriptive summaries will be presented by vital sign and treatment group. Change from BSL will only be summarized for participants with both BSL and post-BSL values and will be calculated as:

change from BSL = post-BSL – BSL

the number and percentage of subjects with newly occurring notable vital signs will be presented. Criteria for notable vital sign abnormalities are provided in Table 2-4 below

Table 2-4 Criteria for notable vital sign abnormalities

Vital sign (unit)	Notable abnormalities
Systolic blood pressure (mmHg)	≥ 140 mmHg or < 90 mmHg
Diastolic blood pressure (mmHg)	≥ 90 mmHg or < 60 mmHg
Pulse (bpm)	> 100 bpm or < 60 bpm

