- 16. Significant medical problems or diseases, including but not limited to the following: uncontrolled hypertension (≥160/95 mmHg), congestive heart failure [New York Heart Association status of class III or IV], uncontrolled diabetes.
- 17. History of renal trauma, glomerulonephritis, or subjects with one kidney only, or a serum creatinine (Scr) level exceeding 1.5 mg/dL (132.6µmol/L).
- 18. Screening total white blood cell(s) (WBC) count <3,000/µL, or platelets <100,000/µL or neutrophils <1,500/µL or hemoglobin <8.5 g/dL (85g/L).
- 19. Active systemic infections during the last two weeks (exception: common cold) prior to randomization.
- 20. History of ongoing, chronic or recurrent infectious disease or evidence of tuberculosis infection as defined by either a positive PPD skin test (the size of induration will be measured after 48-72 hours, and a positive result is defined as an induration of ≥ 5mm or according to local practice/guidelines) or a positive QuantiFERON TB-Gold test as indicated in the assessment schedule. Subjects with a positive test may participate in the study if further work up (according to local practice/guidelines) establishes conclusively that the subject has no evidence of active tuberculosis. If presence of latent tuberculosis is established then treatment according to local country guidelines must have been initiated.
- 21. History or current infection with HIV, hepatitis B or hepatitis C.
- 22. History of lymphoproliferative disease or any known malignancy or history of malignancy of any organ system within the past 5 years (except for basal cell carcinoma or actinic keratoses that have been treated with no evidence of recurrence in the past 3 months, carcinoma in situ of the cervix or non-invasive malignant colon polyps that have been removed).
- 23. Current severe progressive or uncontrolled disease which in the judgment of the clinical investigator renders the subject unsuitable for the trial.
- 24. Inability or unwillingness to undergo repeated venipuncture (e.g., because of poor tolerability or lack of access to veins).
- 25. Any medical or psychiatric condition which, in the investigator's opinion, would preclude the participant from adhering to the protocol or completing the study per protocol.
- 26. Donation or loss of 400 mL or more of blood within 8 weeks before randomization.
- 27. History or evidence of ongoing alcohol or drug abuse, within the last six months before randomization.

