| Systolic Blood Pressure (BP) (mm/Hg) | Either an increase of \ge 30 that results in \ge 180 or $>$ 200 (mm/Hg) OR a decrease of \ge 30 that results in \le 90 or $<$ 75 (mm/Hg) | | | | |
| Diastolic BP (mm/Hg) | Either an increase of \ge 20 that results in \ge 105 or $>$ 115(mm/Hg) OR a decrease of \ge 20 that results in \le 50 or $<$ 40 (mm/Hg) | | | | |

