Neutrophil count decreased	<LLN - 1.5 x 10e9 /L	<1.5 - 1.0 x 10e9 /L	<1.0 - 0.5 x 10e9 /L	<0.5 x 10e9 /L
Lymphocyte count decreased	<LLN - 0.8 x 10e9/L	<0.8 - 0.5 x 10e9 /L	<0.5 - 0.2 x 10e9 /L	<0.2 x 10e9 /L
Creatinine increased*	>1 - 1.5 x baseline; >ULN - 1.5 x ULN	>1.5 - 3.0 x baseline; >1.5 - 3.0 x ULN	>3.0 baseline; >3.0 - 6.0 x ULN	>6.0 x ULN
TBL increased	>ULN - 1.5 x ULN	>1.5 - 3.0 x ULN	>3.0 - 10.0 x ULN	>10.0 x ULN
GGT increased	>ULN - 2.5 x ULN	>2.5 - 5.0 x ULN	>5.0 - 20.0 x ULN	>20.0 x ULN
ALT increased	>ULN - 3.0 x ULN	>3.0 - 5.0 x ULN	>5.0 - 20.0 x ULN	>20.0 x ULN
AST increased	>ULN - 3.0 x ULN	>3.0 - 5.0 x ULN	>5.0 - 20.0 x ULN	>20.0 x ULN
ALP increased	>ULN - 2.5 x ULN	>2.5 - 5.0 x ULN	>5.0 - 20.0 x ULN	>20.0 x ULN
Glucose increased (Hyperglycemia)	>ULN - 8.9 mmol/L	>8.9 - 13.9 mmol/L	>13.9 - 27.8 mmol/L	>27.8 mmol/L
Glucose decreased (Hypoglycemia)	<LLN - 3.0 mmol/L	<3.0 - 2.2 mmol/L >7.75 - 10.34 mmol/L	<2.2 - 1.7 mmol/L >10.34 - 12.92 mmol/L	<1.7 mmol/L
Cholesterol high	>ULN - 7.75 mmol/L			>12.92 mmol/L
Hypertriglyceridemia	1.71 - 3.42 mmol/L	>3.42 - 5.7mmol/L	>5.7 - 11.4 mmol/L	>11.4 mmol/L

* Note: for "creatinine increased" the baseline criteria do not apply

Shift tables will be presented comparing baseline laboratory result (CTCAE grade) with the worst results (expressed in CTCAE grade) during the treatment phase (either initial up to week 16 or entire) analyzed. Of note, baseline will be defined as last assessment prior to first dosing in initial treatment phase.

Summaries for newly occurring or worsening clinically notable lipid abnormalities will also be provided cumulatively for each of the following parameters and categories:

- HDL:
 - <=LLN
 - <0.8x LLN
- LDL, cholesterol, triglycerides:
 - >=UNL
 - >1.5 x ULN

- > 2.5 x ULN

Newly occurring or worsening liver enzyme abnormalities will also be summarized based on the event criteria given in Table 2-3:

Table 2-3 Liver-related events

Parameter	Criterion
ALT	>3xULN; >5xULN; >8xULN; >10xULN, >20xULN
AST	>3xULN; >5xULN; >8xULN >10xULN; >20xULN
ALT or AST	>3xULN; >5xULN; >8xULN >10xULN; >20xULN
TBL	>1.5xULN; >2xULN; >3xULN
ALP	>2xULN; >3xULN; >5xULN
ALT or AST & TBL	ALT or AST >3xULN & TBL >2xULN; ALT or AST >5xULN & TBL >2xULN; ALT or AST >8xULN & TBL >2xULN; ALT or AST >10xULN & TBL >2xULN;
ALP & TBL	ALP >3xULN & TBL >2xULN ALP >5xULN & TBL >2xULN

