3.1 Primary endpoint(s)

As it is a bridging study for China registration, this study will pursue an estimation strategy rather than formal hypothesis testing of treatment difference.

Analysis of the pooled data of global pivotal studies (CAIN457F2312, CAIN457F2318, CAIN457F2336 and CAIN457F2342) showed an active drug response rate of about 51.4% and a placebo response rate of 23.1% after 16 weeks for ACR20. With 40 participants (1:1 ratio to two arms), there are approximately 86.0% probability to show at least 50% global treatment difference (14.15%) and approximately 96.0% probability to show positive treatment difference.

Table 3-1 shows the probability of success with different observed response rates.

Table 3-1 Probability of Success with Different Observed Response Rates

	Observed Response Rate				Criterion 1		Criterion 2	
	Secukinumab (p_1)	Placebo (p_2)	p_1-p_2	95% CI of (p_1-p_2)	Aimed Treatment Difference	PoS	Aimed Treatment Difference	PoS
Scenario 1	0.464	0.231	0.233	(-0.053, 0.519)	> 0.1415	0.772	> 0	0.922
Scenario 2	0.514	0.231	0.283	(-0.003, 0.569)	> 0.1415	0.860	> 0	0.960
Scenario 3	0.564	0.231	0.333	(0.048, 0.618)	> 0.1415	0.922	> 0	0.981
Scenario 4	0.614	0.231	0.383	(0.101, 0.665)	> 0.1415	0.961	> 0	0.992

4 Change to protocol specified analyses

In the protocol, Table 16-1 Clinically notable laboratory values and vital signs summarizes the criteria that will be used to define expanded limits and notable abnormalities of key laboratory tests. The notable BP levels defined in protocol are considered as severe clinical significance that may require follow-up action and reporting as appropriate. In this SAP we use the criteria as defined in Table 2-4. Therefore, the SAP will list all events that BP is out of normal range for reporting purpose.

5 Appendix

Summary statistics for continuous variables will include N, mean, standard deviation, minimum, lower quartile, median, upper quartile, maximum. Summary statistics for discrete variables will be presented in contingency tables and will include absolute and relative frequencies.

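### The SAP's notable-BP table counts only newly occurring values against one upper limit, so severe rises from an already raised baseline drop out and no by-group count of severe BP changes remains

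*SAP*

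**What the plan says.** SAP 2.7.4.2 plans two analyses of vital signs. The first is change from baseline at each visit. The second is a frequency table: "the number and percentage of subjects with newly occurring notable vital signs will be presented". Table 2-4 sets the limits, with a single tier in each direction: systolic "≥ 140 mmHg or < 90 mmHg" and diastolic "≥ 90 mmHg or < 60 mmHg". Newly occurring is not defined.

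Protocol 5.2, item 16, excludes "uncontrolled hypertension (≥160/95 mmHg". Nothing in the eligibility criteria keeps out a participant between 140/90 and that limit.

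Protocol Appendix 16.1, Table 16-1, defines notable BP differently. On the high side it asks for a systolic rise of at least 30 that reaches at least 180, or any value above 200. The diastolic rule is a rise of at least 20 that reaches at least 105, or any value above 115. It has matching rules for falls.

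SAP Section 4 declares the change of criteria. Its reason is: "The notable BP levels defined in protocol are considered as severe clinical significance that may require follow-up action". It then adopts Table 2-4 and states that all out-of-range BP events will be listed.

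**The concern.** A table of newly occurring abnormalities with one threshold is informative only for participants who start below that threshold. The eligibility rule admits participants who start above it. For them, the high-side row is closed from Day 1 on whichever parameter is already raised.

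The protocol's criteria do not have this weakness, because they combine a change from baseline with an absolute level. Section 4 calls those levels severe and then stops using them for the table. What remains is a count that treats a move from 135 to 140 as an event but leaves out a move from 150 to 205.

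Vital signs are named in the secondary safety endpoint. With about 40 participants, a safety reader would want to know how many in each treatment sequence had a severe BP change. The plan as written gives no table with that number.

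**Working it through.** The plan gives no figure to reproduce here, so the check is a classification of example cases.

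**Rules**
- SAP count, high side (usual reading of newly occurring): the post-baseline value is at or above the Table 2-4 limit and the baseline value is below it.
- Protocol Table 16-1, systolic: (rise ≥30 and value ≥180) or value >200.
- Protocol Table 16-1, diastolic: (rise ≥20 and value ≥105) or value >115.
- Every example baseline is below 160/95, so the participant is eligible on BP.

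| Parameter | Baseline → later | Rise | Newly occurring in SAP table | Meets Table 16-1 |
|---|---|---|---|---|
| SBP | 135 → 140 | 5 | yes | no |
| SBP | 139 → 185 | 46 | yes | yes |
| SBP | 140 → 180 | 40 | **no** | **yes** |
| SBP | 150 → 185 | 35 | **no** | **yes** |
| SBP | 150 → 205 | 55 | **no** | **yes** |
| SBP | 159 → 201 | 42 | **no** | **yes** |
| DBP | 89 → 109 | 20 | yes | yes |
| DBP | 90 → 110 | 20 | **no** | **yes** |
| DBP | 94 → 116 | 22 | **no** | **yes** |

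The gap on the high side is therefore baseline SBP from 140 to below 160 and baseline DBP from 90 to below 95. Each parameter is judged separately.

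**Where else such a rise would be reported**
- Listing: SAP Section 4 promises all out-of-range BP events.
- Change from baseline by visit: SAP 2.7.4.2, with minimum and maximum under SAP 2.7.
- Adverse events: only if the finding meets the AE definition. Protocol Table 8-4 leaves the response to abnormal vital signs to the investigator.

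None of these gives a number and percentage of participants with a severe change by group.

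**Internal consistency.** SAP Table 2-1 plans crude incidence of notable vital signs without restricting it to new ones. SAP Table 5-2 takes the most extreme value in a window for notable abnormalities. Section 2.7.4.2 alone says newly occurring. A programmer could build two different tables from this text.

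**Size, as illustration only.** The documents give no BP distribution. Assume mean SBP 122 to 130 (between-person SD 12 to 14, within-person SD 8 to 10) and mean DBP 78 (between-person SD 8 to 9, within-person SD 6 to 7). Also assume a between-person correlation of 0.6 and no drug effect.
- About 15% to 28% of eligible participants would start at or above 140 or 90: 0.15 × 40 = 6 to 0.28 × 40 ≈ 11. This is the number with at least one high-side row closed, not the number of events missed.
- With 17 post-baseline visits and slightly wider diastolic SDs (8 to 10 and 5 to 7), about 0.02% to 0.7% of participants would have a Table 16-1 rise on a parameter already high at baseline: 0.0002 × 40 = 0.008 to 0.007 × 40 = 0.28. By chance alone, that is less than one participant expected in this trial.

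**The case against.** A reader might infer that a severe rise in such a participant would go uncounted everywhere, or that a BP signal could not be seen. The documents do not support that. Section 4 commits to a listing of all out-of-range BP values, and the visit summaries include the maximum. A clinically significant rise would also be an adverse event. In a trial of about 40 participants, a single value of 205 would show in the maximum and in the listing.

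Four further points can be made for the plan.

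- The protocol never promised a table of Table 16-1 counts. Its vital-sign analysis (12.5.2) is change from baseline only, and 10.1.1 treats the Appendix 16.1 limits as alert ranges. The SAP therefore drops no planned tabulation, and Section 4 openly declares the different criteria. This stands. The point is about what the chosen table can show, not about an undeclared deviation.
- Newly occurring is undefined, and Table 2-1 omits it. If the table were programmed from Table 2-1, participants with a raised baseline would be included. This stands too, but it is a reason to settle the wording. A crude count at 140/90 would still not separate severe changes from mild ones.
- Other parts of the SAP are not a clean precedent. For liver tests, "Newly occurring or worsening liver enzyme abnormalities will also be summarized", but against several tiers, so worsening has a meaning there. For ECG, that wording applies only to a listing. The contrast with vital signs is real but weaker than it first looks.
- This SAP covers the final database lock. The placebo-controlled data to Week 16 were reported earlier under a separate plan, safety is descriptive, and no efficacy result is touched. This limits the importance of the point.

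What survives is narrow. On the ordinary reading, the table omits these rises for the parameter concerned, and no other planned output counts severe BP changes by group.

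**Conclusion.** The gap holds on the text, and it is a reporting gap. A participant who enters at or above 140 systolic or 90 diastolic cannot appear as newly notable on the high side of that parameter, and the replaced protocol criteria were the only ones that would have singled out a severe rise. Such a rise would still be visible in the listing and the summaries.

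The conclusion rests on the usual meaning of newly occurring: absent at baseline, present afterwards. The number affected cannot be derived from the documents. The illustration suggests that several participants could have a closed row, while fewer than one severe rise would be missed by chance alone; a drug effect on BP was not modelled. The point merits a SAP clarification. It does not threaten the trial's conclusions, and it implies nothing about the eligibility limit or the handling of raised BP.

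**What to change.** Amend SAP 2.7.4.2 as follows:

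1. Keep Table 2-4 and define newly occurring, stating the baseline used and whether high and low are judged separately.
2. Add rows giving the number and percentage of participants, by treatment sequence, who meet the protocol Table 16-1 systolic and diastolic criteria (change from baseline plus absolute limit), whatever their baseline status under Table 2-4.
3. Make Table 2-1 and Section 4 agree with 2.7.4.2: the same population for the count, both sets of criteria reported, and the out-of-range listing specified in 2.7.4.2 itself.

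Do not simply add the words or worsening to Table 2-4. With one upper limit, worsening has no definition. If it meant any rise, most participants already above the limit would be flagged by ordinary visit-to-visit variation.

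BP readings are already recorded at every scheduled visit from the second screening visit onward, so no new data are needed. The cost is some SAP wording and a slightly longer table. No eligibility or clinical management threshold changes.

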2.8 Patient-reported outcomes

SF-36

The following variables will be evaluated:

- SF-36 domain scores (based on a scale of 0-100)
- SF-36 PCS [REDACTED] scores (norm-based scores)
- [REDACTED]

For the change in SF-36 summary scores (PCS [REDACTED]), summary statistics will be provided using observed data for each treatment regimen.

[REDACTED]

The SF-36 domain scores will be summarized by treatment.

[REDACTED]

[REDACTED]

[figure not shown]
Patient's global assessment of disease activity (PaGA)

Summary statistics of observed data by visit and change from BSL in PaGA will be provided for each treatment.

Patient's assessment of PsA pain

Summary statistics of observed data by visit and change from BSL in Patient's assessment of PsA pain will be provided for each treatment.

[REDACTED]

2.10 Interim analysis

Interim analysis is not applicable in this study.

The primary endpoint analysis was performed after all participants have completed the Week 16 visit or discontinued earlier. The primary endpoint analysis was used for regulatory submission. The investigators, site personnel and monitors will continue to remain blinded to the original treatment assignment that each participant received at randomization until after the database lock for Week F60 analysis.

Subsequent to the primary endpoint analysis, the final analysis is planned after all participants have completed the Week F60 assessments and may be used for regulatory submission and/or publication purposes. Additional analyses may be performed to support interactions with health authorities, as necessary.

3 Sample size calculation

3.1 Primary endpoint(s)

As it is a bridging study for China registration, this study will pursue an estimation strategy rather than formal hypothesis testing of treatment difference.

Analysis of the pooled data of global pivotal studies (CAIN457F2312, CAIN457F2318, CAIN457F2336 and CAIN457F2342) showed an active drug response rate of about 51.4% and a placebo response rate of 23.1% after 16 weeks for ACR20. With 40 participants (1:1 ratio to two arms), there are approximately 86.0% probability to show at least 50% global treatment difference (14.15%) and approximately 96.0% probability to show positive treatment difference.

Table 3-1 shows the probability of success with different observed response rates.

Table 3-1 Probability of Success with Different Observed Response Rates

	Observed Response Rate				Criterion 1		Criterion 2	
	Secukinumab (p_1)	Placebo (p_2)	p_1-p_2	95% CI of (p_1-p_2)	Aimed Treatment Difference	PoS	Aimed Treatment Difference	PoS
Scenario 1	0.464	0.231	0.233	(-0.053, 0.519)	> 0.1415	0.772	> 0	0.922
Scenario 2	0.514	0.231	0.283	(-0.003, 0.569)	> 0.1415	0.860	> 0	0.960
Scenario 3	0.564	0.231	0.333	(0.048, 0.618)	> 0.1415	0.922	> 0	0.981
Scenario 4	0.614	0.231	0.383	(0.101, 0.665)	> 0.1415	0.961	> 0	0.992

4 Change to protocol specified analyses

In the protocol, Table 16-1 Clinically notable laboratory values and vital signs summarizes the criteria that will be used to define expanded limits and notable abnormalities of key laboratory tests. The notable BP levels defined in protocol are considered as severe clinical significance that may require follow-up action and reporting as appropriate. In this SAP we use the criteria as defined in Table 2-4. Therefore, the SAP will list all events that BP is out of normal range for reporting purpose.

5 Appendix

Summary statistics for continuous variables will include N, mean, standard deviation, minimum, lower quartile, median, upper quartile, maximum. Summary statistics for discrete variables will be presented in contingency tables and will include absolute and relative frequencies.

5.1 Visit window

5.1.1 Visit window

When visit windows are used, all visits will be re-aligned, i.e., they will be mapped into one of the visit windows. E.g., if the Week 4 visit of a subject is delayed and occurs on Day 46 instead of on Day 29, say, it will be re-aligned to visit window Week 8. In case of major deviations from the visit schedule, or due to unscheduled visits, several assessments of a subject may fall in a particular visit window (either scheduled or unscheduled). Statistical approaches to handle multiple assessments in a given visit window are specified in Table 5-2.

For lab/ECG/vital signs, as for follow-up (F/U) visits, only assessments that come as F/U nominal visit will be directly assigned as analysis F/U visit. Other assessments that are beyond the last on-treatment visit (Week 60) or after nominal F/U visit date will be listed under label “Week 60” in the listing.

For chemistry, hematology, urinalysis and lipids, the F/U visit will be presented in the summary table to present long-term safety of AIN. Of note, participants are allowed to have gaps in visits. All data collected will be displayed in listings.

Table 5-1 Analysis visit windows

Analysis visit	Target Day	Group 1	Group 2	Group 3	Group 4	Group 5	Group 6	Group 7	Group 8	Group 9
Baseline	1	≤ 1	≤ 1	≤ 1	≤ 1	≤ 1	≤ 1	≤ 1	≤ 1	≤ 1
Week 1	8	2-11						2-11		
Week 2	15	12-18						12-18		
Week 3	22	19-25						19-25		
Week 4	29	26-43		2-43	2-43	2-57		26-43		
Week 8	57	44-71		44-71	44-71			44-71	2-85	
Week 12	85	72-99	2-99	72-99	72-99	58-99		72-99		
Week 16	113	100-127	100-155	100-141	100-141	2-239	100-127	86-141	2-239	
Week 20	141	128-155						128-155		
Week 24	169	156-183		142-267	142-197	142-197		156-183	142-267	
Week 28	197	184-211	156-239					184-211		
Week 32	225	212-239			198-253	198-253		212-239		
Week 36	253	240-267						240-267		
Week 40	281	268-295	240-323		254-323	254-323		268-295		
Week 44	309	296-323						296-323		
Week 48	337	324-351						324-351		
Week 52	365	352-435	324-393	268-435	324-435	324-393	240-393	352-393	268-393	240-435

*The first administration of randomized study treatment (first dose) is defined as Day 1.

Group 1: ACR components, ESR, High sensitivity C-Reactive protein

Group 2: Hematology, blood chemistry, urinalysis

Group 3: SF-36 v2

Group 4: [REDACTED] [REDACTED] [REDACTED], Patient's global assessment of psoriasis and arthritis disease activity (VAS)

Group 5: Pregnancy test

Group 6: ECG, Body weight

Group 7: Vital signs

Group 8: Lipids

Group 9: ANA, anti-dsDNA

The following rules are used to determine the window for an applicable visit post baseline
“Lower limit” = “upper limit of prior applicable visit” + 1. “Upper limit” = “target day of current visit” + integer part of (“target day of next applicable visit” - “target day of current visit”)/2. Lower limit of the first applicable visit is always Day 2. Day 1 is the date of the first dose of randomized study treatment.

The mapping described above applies to all visits (not just scheduled visits). Repeat and/or unscheduled visits (which will be numbered in the database according to new NCDS standards) will be mapped for analysis purposes in the same way as scheduled visits. This leaves the possibility, then, for multiple measurements within an analysis window. If more than one assessment falls into the interval, the rules defined in Section 5.1.2 below are applied.

Re-randomization will be performed at the end of treatment period 1, assessment from treatment period 2 will not be considered for treatment period 1, e.g., if a Week 20 (scheduled visit) measurement would fall into the Week 16 visit window, this measurement would not be analyzed as treatment period 1 value. Of note, for subjects who discontinue in treatment period 1, i.e., not moving into treatment period 2, measurements taken in follow-up period would still be considered for treatment period 1.

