Novartis will provide to investigators in a separate document a proposed informed consent form that complies with the International Council for Harmonization of Technical Requirements for Pharmaceuticals for Human Use (ICH) GCP guidelines and regulatory requirements and is considered appropriate for this study. Any changes to the proposed consent form suggested by the investigator must be agreed by Novartis before submission to the IRB/IEC.

Information about common side effects already known about the investigational drug can be found in the Investigator's Brochure (IB). This information will be included in the participant informed consent and should be discussed with the participant during the study as needed. Any new information regarding the safety profile of the investigational drug that is identified between IB updates will be communicated as appropriate, for example, via an investigator notification or an aggregate safety finding. New information might require an update to the informed consent and then must be discussed with the participant.

Women of child bearing potential must be informed that taking the study treatment may involve unknown risks to the fetus if pregnancy were to occur during the study, and agree that in order to participate in the study they must adhere to the contraception requirements (see Section 5.2).

A copy of the approved version of all consent forms must be provided to Novartis after IRB/IEC approval.

Participants might be asked to complete an optional questionnaire to provide feedback on their clinical trial experience.

8 Visit schedule and assessments

The Assessment Schedule (Table 8-1) lists all of the assessments when they are performed. All data obtained from these assessments must be supported in the participant's source documentation.

Participants should be seen for all visits/assessments as outlined in the assessment schedule (Table 8-1) or as close to the designated day/time as possible.

- For visits scheduled through Week 4, the study treatment should not be administered less than 7 days from the previous administration.
- For visits scheduled after Week 4, the study treatment should not be administered less than 14 days from the previous administration

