12.4.3 Handling of missing values/censoring/discontinuations

Missing data for ACR20 response and other binary efficacy variables (e.g., ACR50, etc.) for data up to Week 16 will be handled as follows:

- 1. participants who discontinue from treatment or study for any reason will be considered as non-responders from the time of discontinuation through Week 16
- 2. participants who do not have the required data to compute ACR responses (i.e., tender and swollen joint counts and at least three of the five ACR core set variables) at BSL and at the specific timepoint will be classified as non-responders at the specific timepoint.

participants who are unblinded prior to the scheduled time point will be considered nonresponders from the time of unblinding up to Week 16. The primary analysis will use the nonresponder imputation.

Continuous variables (e.g., ACR components, etc.) will be analyzed using a mixed-effects model repeated measures (MMRM) which is valid under the missing at random (MAR) assumption. As such, single-point imputation of missing data will not be performed (e.g., LOCF). For analyses of these parameters, if all post-BSL values are missing then these missing values will not be imputed and this participant will be removed from the analysis of the corresponding variable, i.e., it might be that the number of participants providing data to an analysis is smaller than the number of participants in the FAS.

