5.2.3 Psoriatic Arthritis Disease Activity Score (PASDAS)

PASDAS is a new composite measure developed to access disease activity in Psoriasis (GRACE Project) (Helliwell et al 2012). It is calculated by utilizing seven measures; the seven components are: Patient reported measures [REDACTED]

[REDACTED] skin, peripheral joint counts (Tender and Swollen joint counts), [REDACTED] acute phase response (CRP) and Patient & Physician global VAS scores.

$$\begin{aligned} \text{PASDAS} = & (0.18 \times \sqrt{\text{Physician global VAS}}) \\ & + (0.159 \times \sqrt{\text{Patient global VAS}}) \\ & - (0.253 \times \sqrt{\text{SF36-PCS}}) \\ & + (0.101 \times \text{LN}(\text{Swollen joint count} + 1)) \\ & + (0.048 \times \text{LN}(\text{Tender joint count} + 1)) \\ & [REDACTED] \\ & [REDACTED] \\ & + (0.102 \times \text{LN}(\text{CRP} + 1)) + 2) * 1.5 \end{aligned}$$

If any component measurement is missing, PASDAS will be missing. The patient global VAS defined in the PASDAS score is “VAS for PASDAS assessment” which measures patient’s global assessment of PSORIASIS and ARTHRITIS disease activity. The Physician global VAS is the Physician’s global assessment of PsA disease activity. Tender Dactylitis count is from “Leeds Dactylitis Instrument” CRF page with “Was dactylitis present?” = “Yes” and “Tender/non-tender” = “Tender”.

[figure not shown]
[figure not shown]
66-swollen / 68-tender joint counts for PASDAS assessment:

[figure not shown]
There are only 66 swollen and 68 tender joint counts which will be used for PASDAS assessment. That is the 10 joints in CRF: CMC1, DIP2 (FOOT), DIP3 (FOOT), DIP4 (FOOT), and (DIP5 (FOOT) both left and right, should not be counted in the swollen/tender joint count in PASDAS formula.

[figure not shown]
[figure not shown]
If the number of joints for which data were available (e.g., T) is less than 66/68 for the swollen/tender joint assessment, the number of swollen/tender joints (e.g., t) will be scaled up proportionately (i.e., $66*t/T$ or $68*t/T$ for swollen or tender joint count).

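### SAP Table 5-1 can relabel a late Week 16 visit, held before re-randomisation, as Week 20, so pre-switch data may be reported under the post-switch treatment sequence (minor)

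*SAP*

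**What the plan says.** SAP 5.1.1 states that, where visit windows are used, "all visits will be re-aligned, i.e., they will be mapped into one of the visit windows". Its own example, in which the visit ends up in Week 8, shows that the study day overrides the nominal visit: "if the Week 4 visit of a subject is delayed and occurs on Day 46 instead of on Day 29, say, it will be re-aligned". Table 5-1 lists "Group 1: ACR components, ESR, High sensitivity C-Reactive protein", with Week 16 as Day 100-127 and Week 20 as Day 128-155. Group 3 (SF-36) and Group 4 (which includes the patient's psoriasis and arthritis VAS) have Week 16 as Day 100-141.

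One rule deals with the boundary between treatment periods: "assessment from treatment period 2 will not be considered for treatment period 1". No rule covers the reverse.

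SAP Table 5-2 selects among values already inside a window. If a participant switches from placebo to secukinumab in a window after Week 16, its efficacy row prefers the value nearest the target after the switch. If there is none, it uses the nearest value before the switch.

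At Week 16, assessments come before re-randomisation (Protocol 6.3.2) and before dosing (Protocol 6.7.2). Protocol Section 8 gives no visit tolerance in days; visits are to be on schedule "or as close to the designated day/time as possible". Participants without the required ACR data at a timepoint "will be classified as non-responders at the specific timepoint" (Protocol 12.4.3). On the composite score, SAP 5.2.3 says: "If any component measurement is missing, PASDAS will be missing".

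**The concern.** A Week 16 visit on, say, Day 130 reflects Period 1 treatment only, because the participant is assessed first and re-randomised afterwards. The SAP nevertheless files its joint counts, global assessments, pain, HAQ-DI, CRP and ESR under Week 20.

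The final analysis summarises data after Week 16 by treatment sequence (SAP 2.1). If no other Week 20 value exists, an assessment made on placebo can therefore be reported as Week 20 data in a placebo-to-secukinumab sequence. Table 5-2 provides for this explicitly through its fallback. If a later value does exist, the end-of-Period-1 assessment can drop out of the by-visit summaries. The same visit can also be split between two analysis visits, which matters for PASDAS.

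**Working it through.** **1. Reproduce the windows.** SAP 5.1.1 sets the upper limit as the target day plus the integer part of half the distance to the next applicable target. The lower limit is the previous upper limit plus 1. Target days are from Table 5-1.

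- Group 1, Week 12 upper: 85 + int((113 − 85)/2) = 99, so Week 16 opens on Day 100.
- Group 1, Week 16 upper: 113 + int((141 − 113)/2) = 127, so Week 20 opens on Day 128.
- Group 1, Week 20 upper: 141 + int((169 − 141)/2) = 155.
- Groups 3 and 4, Week 16 upper (next applicable visit is Week 24): 113 + int((169 − 113)/2) = 141.

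All four agree with Table 5-1.

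**2. Place a late visit.** Against the SAP target of Day 113, 14 days late is Day 127 (Week 16), 15 to 42 days late is Day 128-155 (Week 20), and 43 days late is Day 156 (Week 24). The protocol schedule puts Week 16 at Day 112; counted from there, the Week 20 label starts at 16 days late.

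**3. Follow a Day 130 visit through Table 5-2.** Protocol Section 8 asks for at least 14 days between doses after Week 4, so the next dose falls on Day 144 or later.

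- A next assessment on Day 144 is |144 − 141| = 3 days from the Week 20 target, against |130 − 141| = 11 for the Day 130 value. The later value is used and the Day 130 value drops out. For placebo switchers, the preference for post-switch values gives the same result.
- With no other assessment in Day 128-155, the Day 130 value is reported as Week 20. For placebo switchers this happens through the stated fallback; for participants first assigned to secukinumab it is the only value in the window.

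**4. Split of one visit.** For Day 128-141, SF-36 and the psoriasis/arthritis VAS remain Week 16, while joint counts, physician's global assessment and CRP become Week 20. If PASDAS is assembled from windowed components, its Week 16 value is missing. From Day 142, Groups 3 and 4 also leave Week 16 (for Week 24).

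**5. Conditional size for ACR20.** This applies only if the primary-endpoint SAP used the same windows and nothing else falls on Day 100-127. Inputs from SAP 3.1: 20 per arm, response rates 51.4% and 23.1%, threshold 14.15 points. Exact enumeration of two binomials gives a probability of 0.860 of exceeding the threshold, matching SAP Table 3-1. One lost responder is 1/20 = 5 points in that arm. In the table, an affected participant counts as a non-responder with the denominator kept at 20; the share of late visits is an assumption.

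| Case | Expected difference (points) | P(difference > 14.15 points) |
|---|---|---|
| None affected | 51.4 − 23.1 = 28.3 | 0.860 |
| 5% of visits, both arms | 28.3 × 0.95 = 26.9 | 0.840 |
| 10% of visits, both arms | 28.3 × 0.90 = 25.5 | 0.817 |
| One secukinumab participant | 51.4 × 19/20 − 23.1 = 25.7 | 0.822 |
| One placebo participant | 51.4 − 23.1 × 19/20 = 29.5 | 0.879 |
| One in each arm | 28.3 × 19/20 = 26.9 | 0.844 |

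**The case against.** A reader might infer that any participant whose Week 16 visit is 15 or more days late becomes an ACR20 non-responder in the primary analysis. The documents do not support that. SAP Section 1 limits this SAP to the final database lock and says Week 16 analyses are not repeated. SAP 2.5.2 to 2.5.4 refer the primary model, missing-data handling and supportive analyses to a separate SAP that is not supplied. Nothing available shows that Table 5-1 governed that analysis. The inference also fails if another assessment, such as a late Week 12 visit or an unscheduled one, falls on Day 100-127. The Week 20 label itself stops at Day 155. These objections stand.

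Other points also carry weight. Midpoint windows are conventional, and Day 130 is nearer to the Week 20 target (11 days) than to the Week 16 target (17 days). A Week 16 dose on Day 128 leaves only 13 days to Day 141, below the protocol's 14-day minimum, so such a visit is a marked schedule deviation, and the documents report none. No window group names PASDAS, so building it from windowed components is an inference. DAS28-CRP and HAQ-DI at Week 16 are planned for MMRM under missing at random (Protocol 12.4.3 and 12.5.1), so earlier visits would still contribute. SAP 5.1.1 keeps all collected data in listings.

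None of this supplies the missing protection. The windows, the one-directional rule and the fallback are all in the SAP that governs the final analysis.

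**Conclusion.** The gap is real and minor. As written, the SAP permits a pre-switch assessment made on Day 128-155 to be reported as Week 20 data under the post-switch sequence, or to be displaced by a later value. Week 16 PASDAS is also lost for Day 128-141 if the score uses windowed components.

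The ACR20 consequence is conditional on an SAP that is not available and on an otherwise empty Week 16 window. Its frequency is unknown and its direction is not fixed: among the single-participant cases above, the probability of exceeding 14.15 points ranges from 0.822 to 0.879 against the planned 0.860. The study follows an estimation strategy, so no formal test is at stake. The calculation shows possible size only; it is not evidence that the primary result was affected.

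**What to change.** - Add to SAP 5.1.1 that assessments made on or before re-randomisation, and before the first Period 2 dose, are not considered for Period 2. For participants entering Period 2, the last such assessment stays in the Week 16 window for every efficacy group, so that PASDAS components remain together. Flag any such visit on Day 128 or later.
- Remove the fallback to pre-switch values for windows after Week 16 in the efficacy row of Table 5-2. A Week 20 value with no post-switch measurement should be missing.
- Confirm whether the primary-endpoint SAP used these windows, and check the completed Week 16 listing for nominal Week 16 visits on Day 128 or later. If there are any, show ACR20, DAS28-CRP, HAQ-DI and PASDAS with and without them as a sensitivity display.

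The cost is a few lines in the SAP, a small change to the visit mapping and one listing check. The downside is that some Week 16 values will come from later than the nominal window. The proposed rule sets no upper limit on lateness, which is why the flag and the with-and-without display are needed.
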